6.1 Description

We will use Black and Mild cigarillos (plastic-tipped) given that they are the most popular brand in the marketplace and with young adults. We chose one cigarillo brand to standardize the exposure across participants. Swisher is also a popular cigarillo brand. However, qualitative research suggests that the Swisher brand, especially the untipped variety, is typically used for making blunts, while Black and Mild cigarillos are rarely used for blunting. The flavored Black and Mild cigarillos will include citrus fruit ("Jazz") and cream. We chose two of the most popular sweet flavors on the market and those likely to remain on the market, promoting generalizability and the avoidance of exposure to aversive flavoring. We are not seeking to examine the rewarding and reinforcing value of specific flavors. The non-flavored cigarillo (tobacco without characterizing flavors) will be Black and Mild Classic (plastic-tipped).

We chose to compare sweet flavored cigarillos to non-flavored tobacco cigarillos because they are most popular among young adults. It is important to note that some cigarillos without sweet

CONFIDENTIAL

This material is the property of the University of Pennsylvania. Do not disclose or use except as authorized in writing by the study sponsor

characterizing flavors can have significant levels of high-intensity sweeteners, especially if they are untipped or wood-tipped. As such, we chose plastic-tipped Black and Mild Classic cigarillos (0 mg sugar equivalents/cm²) versus Black and Mild Sweets (6.3 mg sugar equivalents/cm²) as the comparator.

6.2 Distribution Schedule

Participant will: (1) sample three cigarillos (2 puffs from each) at Laboratory Visit 1; (2) take a total of 10 puffs from a flavored and/or unflavored cigarillo at Laboratory Visit 2; and (3) typically smoke 0 – 2 cigarillos across a 90 minute ad-lib smoking session at Laboratory Visit 3.

6.3 Receipt, Storage, Dispensing and Destruction

Staff will purchase the cigarillos from previously approved tobacco vendors in Philadelphia. Cigarillos will be maintained at room temperature in a double-locked location (e.g., a locked cabinet in a locked room). A master product accountability log will be maintained throughout the study. All product received, distributed to each unique participant, and destroyed will be documented per standardized product accountability procedures. At the completion of the study, there will be a final reconciliation of cigarillos purchased, dispensed, and cigarillos remaining. This reconciliation will be logged on a study completion reconciliation form. Any notable discrepancies will be investigated, documented, and resolved if possible.

7 Study Procedures

7.1 Telephone Eligibility Screen

Individuals interested in study participation will be screened by a qualified member of the research team to determine initial study eligibility. If the participant meets preliminary eligibility, they will be invited to schedule Laboratory Visit 1 at which their final eligibility will be confirmed.

7.2 In-Center Visits

7.2.1 Visit Reminders

Participants will typically receive study visit reminders 48 to 24 hours prior to their scheduled study visits via phone call, email, and text message (if applicable).

7.2.2 Laboratory Visit 1

During Laboratory Visit 1, (Duration: ~2 hours) participants will:

1. Either hear an informed consent and HIPAA presentation where all the study procedures and institutional policies will be reviewed OR complete a virtual IRB-approved informed consent and HIPAA presentation via REDCap where all the study procedures and institutional policies will be reviewed prior to coming in to complete the remainder of Laboratory Visit 1. The Principal Investigator will determine whether in-person or electronic consent will be collected based on University COVID-19-related guidelines. The in-person consent procedures will proceed as follows: the combined informed consent and HIPAA form will be read verbatim. All participant questions will be answered as appropriate after which the combined informed consent and HIPAA form will be completed (signed and dated) by both the participant and a qualified member of the research team. The electronic consent process will involve the following procedures:
 - a. The participant will be required to view the entire combined informed consent and HIPAA form on REDCap prior to signing the document. Upon completing their reading of the consent, the participant will be offered the opportunity to indicate if they have any questions and a staff member will call the participant to complete a

CONFIDENTIAL

This material is the property of the University of Pennsylvania. Do not disclose or use except as authorized in writing by the study sponsor

consent discussion via the telephone. All participant questions will be recorded and answered as appropriate after which the combined informed consent and HIPAA form will be completed (virtually signed and dated) by both the participant and a qualified member of the research team.

- b. The staff will print a signed copies of this completed record and provide one copy to the participant and save one copy for our records.
2. Confirm the accuracy of information (i.e., name, address, phone number, email [if applicable], date of birth, age, gender, ethnicity, and race) provided during the initial Telephone Eligibility Screen.
3. Complete a UDS (at least 30ml [two tablespoons] of urine). The UDS will assess the use of any study-prohibited medications/recreational drugs (See Key Exclusionary Criteria; Alcohol and Drug). Participants who test positive for any exclusionary medications or recreational drugs per this protocol will be deemed ineligible.
 - a. The UDS sample will also be used for urine cotinine analysis.
4. Female participants only: Self-administer a CLIA-waived urine pregnancy test. Female participants are advised that participation of pregnant women in this study is prohibited and that they may withdraw at any time.
5. Perform a BrAC assessment to control for alcohol consumption. Participants with a BrAC greater than 0.000 at Laboratory Visit 1 will be ineligible.
6. Perform a CO breath assessment and collect self-report smoking behavior over the past 24 hours to control for prior tobacco exposure.
7. Answer questions about use of marijuana, other tobacco products (besides cigarettes), or vaping of any substance including tobacco/nicotine or other drugs in the past month.
8. Complete measures of Demographics, Smoking History (e.g., duration, rate, regular and/or menthol), FTND (Fagerstrom Test of Nicotine Dependence), and HONC (Hooked on Nicotine Checklist)
9. Complete a Medical History Form with a member of the research team to review for applicable contraindications, including psychiatric exclusions, previously listed under Inclusion and Exclusion Criteria (section 4.3 and 4.4).
10. Complete a baseline concomitant medication review (if applicable).
11. Complete questionnaires:
 - a. Adverse Events Form (Open-Ended AEs)
 - b. Depression, sensation-seeking, risk beliefs, cigarillo advertising and marketing exposure
12. Use study-provided cigarillos during a session in our smoking lab (required). During this smoking task, participants will sample two puffs from each of three cigarillos. Sampling of each cigarillo will be separated by 20 minutes and the order will be counterbalanced.
13. Be reminded to engage in tobacco abstinence (e.g., combustible cigarettes, e-cigarettes, cigars, blunts) and combustible marijuana abstinence for 10 hours in preparation for Laboratory Visit 2.
14. Tentatively schedule next study visit with a member of the research team.

7.2.3 Laboratory Visit 2

During Laboratory Visit 2, (Duration: ~ 2 hours) participants will:

1. Arrive at the Center at approximately 1:00 PM after having abstained from tobacco (e.g., combustible cigarettes, e-cigarettes, cigars, blunts) and combustible marijuana for 10 hours prior to visit.
2. Provide a carbon monoxide (CO) breath sample: abstinence verified by a CO measurement of < 10 ppm or < 50% of Visit 1's CO value
3. Provide a 30ml (2 tablespoons) urine sample to conduct cotinine analysis: abstinence verified by a cotinine reading < Visit 1's cotinine value; participants already measuring in the lowest tier are expected to remain there
4. Complete concomitant medication review

CONFIDENTIAL

This material is the property of the University of Pennsylvania. Do not disclose or use except as authorized in writing by the study sponsor

5. Complete forms re: use of marijuana, other tobacco products (besides cigarettes), or vaping of any substance including tobacco/nicotine or other drugs in the past month
6. Complete Adverse Events Form (Open-Ended AEs)
7. Be introduced to and briefly practice the Relative Reinforcing Value of Flavoring (RRVF) computerized lab task.
8. Complete computerized lab task: Relative Reinforcing Value of Flavoring (RRVF).
9. Use study-provided cigarillos during a session in our smoking lab (required). Following the RRVF task, participants will take earned cigarillo puffs, then complete a standardized one-hour wait period in the laboratory.
10. Be reminded to engage in tobacco abstinence (e.g., combustible cigarettes, e-cigarettes, cigars, blunts) for 10 hours in preparation for Laboratory Visit 3.
11. Tentatively schedule next study visit with a member of the research team.

7.2.4 Laboratory Visit 3

During Laboratory Visit 3, (Duration: ~ 2.5 hours) participants will:

1. Arrive at the Center at approximately 1:00 PM after having abstained from tobacco (e.g., combustible cigarettes, e-cigarettes, cigars, blunts) and combustible marijuana for 10 hours prior to visit
2. Provide a carbon monoxide (CO) breath sample: abstinence verified by a CO measurement of < 10 ppm or < 50% of Visit 1's CO value
3. Provide a 30ml (2 tablespoons) urine sample to be used for urine cotinine analysis: abstinence verified by a cotinine reading < Visit 1's cotinine value; participants already measuring in the lowest tier are expected to remain there
4. Complete concomitant medication review
5. Complete forms re: use of marijuana, other tobacco products (besides cigarettes), or vaping of any substance including tobacco/nicotine or other drugs in the past month
6. Complete Adverse Events Form (Open-Ended AEs)
7. Begin a 90 minute cigarillo smoking ad libitum session, followed by a 30 minute period of no smoking. During this portion of the visit, the participant will be required to use study-provided cigarillos during a session in our smoking lab.
8. Be provided with resources on tobacco cessation services. Participants will also review an educational and prevention materials that explain the study rationale and the importance of cigarillo cessation, and the role that flavoring may play in future cigarillo use.

CONFIDENTIAL

This material is the property of the University of Pennsylvania. Do not disclose or use except as authorized in writing by the study sponsor

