4.2 Study Duration

Recruitment/enrollment is anticipated to begin in August 2021 and will continue for 18 months. We estimate that up to 86 participants will have completed the study by February 2023. Visits 1-3 will be completed within a 2-3 week time period. Each participant will be considered “active” until they have completed all three laboratory visits.

4.3 Laboratory Visit 1

Participants will arrive at the BBL at approximately 1:00PM. Eligible participants will document their tobacco use that day (number, time, type) and complete lifetime and past 30 day measures of cigarillo use (flavored, non-flavored, preference), tobacco use history (e.g., cigarette smoking and menthol status), as well as baseline measures of marijuana use, depression, sensation-seeking, cigarillo risk beliefs, exposure to cigarillo flavor marketing, and demographics. Participants will provide a carbon monoxide (CO) sample and a urine sample to conduct urine cotinine analysis.

Subjective rewarding value of cigarillo flavoring. Participants will be exposed to three cigarillos. Participants who are eligible and elect to participate in the study will be required to use the study-provided cigarillos during this portion of the visit in our smoking lab. One cigarillo will be non-flavored, meaning no characterizing flavors were added to the tobacco. Two will contain sweet flavoring (fruit and cream). All three will have the same characteristics, only differing by flavor. Participants will take 2 puffs from the non-flavored cigarillo, the fruit-flavored cigarillo, and the cream-flavored cigarillo. The exposure to the three cigarillos will be separated by 20 minutes each, and the order of the three exposures will be counterbalanced. Order will be stratified by sex and smoking status. After each of the three cigarillo exposures, participants will complete measures of subjective reward. Visit 1 will occur in the afternoon versus the morning to increase the likelihood that participants who smoke cigarettes smoke normally throughout the day and can rate flavoring/no flavoring in the absence of significant withdrawal symptoms. After Visit 1, participants will be scheduled for Visit 2. Participants who use tobacco (e.g., combustible cigarettes, e-cigarettes, cigars, blunts) or combustible marijuana will be given instructions to abstain from tobacco products and combustible marijuana 10 hours prior to BBL Visit 2.

CONFIDENTIAL

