The participant will then begin a 90-minute ad-libitum cigarillo smoking paradigm for the assessment of the absolute reinforcing value of a sweet flavored cigarillo. Participants will be taken to a specially ventilated and approved smoking research room equipped with a sofa and table. Participants will be told that they will have a 90-minute laboratory waiting session where they can choose to smoke any of the color coded cigarillos placed on the table in the lab while they periodically complete questionnaires while they wait. Participants will be told that the 90-minute laboratory session will be followed by a 30-minute period of enforced abstinence from tobacco use. The labeled and color coded cigarillos will be placed on a table next to the couch. To limit brand affiliation and expectancy, the cigarillo brand identifier will be covered with tape when we color code the cigarillo for flavoring. A clock will be placed on the table showing minutes elapsed from 90 minutes. The number of cigarillo puffs (sweet flavored versus non-flavored) is the outcome variable, with consumption reflecting the absolute reinforcing value of the flavored cigarillo. Participants will be observed via an observation window by a trained research assistant who will monitor and count the number of cigarillo puffs taken (from each cigarillo) during the 90-minute period. The ad-lib session will be videotaped to independently score the number of puffs taken.

At the end of the visit, a member of the research staff will provide participants with resources on tobacco cessation services. Participants will also review educational and cigarillo cessation prevention materials that explain the study rationale and the importance of cigarillo cessation, especially as it pertains to flavored cigarillos.

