Breath Alcohol Concentration (BrAC): Participants will complete a BrAC assessment at Laboratory Visit 1. Participants will be made aware of the BrAC assessment prior to the visit and asked to avoid alcohol and alcohol-based products (e.g. mouthwash, breath spray, etc.) the evening and morning before Laboratory Visit 1. The BrAC monitor is a handheld device that uses a disposable mouthpiece and reports the concentration of alcohol in exhaled breath. Any reading greater than 0.000 indicates alcohol consumption within the last 14 hours. Participants with a BrAC greater than 0.000 at Laboratory Visit 1 will be deemed ineligible.

Medical History Form: A medical history form (led by the research staff) will be completed to review for applicable contraindications previously listed under Key Inclusion/Exclusion Criteria at Laboratory Visit 1.

Demographics and Smoking History: Standard surveys will collect demographics information such as age, sex, race, ethnicity, education level, and income. Standard survey questions will assess cigarillo use history (number and flavored), use of other combustible products, as well as cigarette smoking history (e.g., age at initiation, current smoking rate). Nicotine dependence will be assessed with the Fagerstrom Test for Nicotine Dependence (FTND). This 6-item measure has good internal consistency ($\alpha = .64$) and high test-retest reliability. Nicotine dependence will also be assessed using the Hooked on Nicotine Checklist (HONC).

Adverse Events Form (Open-Ended AEs): Participants will be asked an open-ended question about any symptom or medical event that may be related to their study participation. These events will be documented as **unanticipated (unexpected) AEs** unless they are otherwise outlined in the protocol and/or consent form (i.e. related to withdrawal, assessments, etc.). The reporting period for each assessment will inquire about any event(s) or symptom(s) experienced since the last in-person visit. If a participant reports a symptom or medical event, they will be asked to rate the severity of the

CONFIDENTIAL

This material is the property of the University of Pennsylvania. Do not disclose or use except as authorized in writing by the study sponsor

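### The only adverse event form scheduled at Visit 3 comes before the ad-lib smoking session and no contact follows, so no AE query is scheduled for that session

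*Combined protocol and SAP*

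**What the plan says.** Section 7.2.4 lists eight steps for Visit 3. Step 6 is the AE form ("Complete Adverse Events Form (Open-Ended AEs"). Step 7 is the smoking session: "Begin a 90 minute cigarillo smoking ad libitum session, followed by a 30 minute period of no smoking". Step 8 begins "Be provided with resources on tobacco cessation services" and adds educational material; it is the last step.

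Section 7.4.1 sets the form's look-back: "The reporting period for each assessment will inquire about any event(s) or symptom(s) experienced since the last in-person visit". Section 9.2.1 repeats this. Under section 4.2 a participant is active "until they have completed all three laboratory visits", and no later visit or call is scheduled.

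Section 9.1 runs the AE reporting period to the end of the study. Section 9.2.1 says that all AEs in that period will be captured by its listed methods. Two of these bring events to light: the open-ended form, and spontaneous reports by the participant. The third item there, the AE Note, is a source document. Section 8.1 names nausea, dizziness and rapid heartbeat as possible effects of the puffs and describes them as usually mild and brief.

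**The concern.** At each visit the AE form comes before smoking. That works at Visits 1 and 2, because the next visit's form looks back over the session. Visit 3 has no next visit. Followed as written, the one session whose puff count is left to the participant is also the one session after which no AE form is scheduled for anybody.

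What is at stake is the AE record. The form asks about any symptom that may be related to participation, whereas the spontaneous route asks for symptoms that the participant finds notable. Brief nausea or dizziness could be reported on the first and go unmentioned on the second. A Visit 3 record with no AE could then mean that there were no symptoms, or that no one asked.

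**Working it through.** No sample-size, power or alpha figure bears on this point. The check is a trace of AE forms against smoking sessions, followed by some simple counts.

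**1. Is the Visit 3 list in time order?** It is not expressly called chronological. Step 1 is arrival, the abstinence checks come before smoking, and section 4.5 places the step 8 material at the end of the visit. Reading it in time order is reasonable.

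**2. Forms against sessions (sections 7.2.2 to 7.2.4, 8.1 and 6.2)**

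| Visit | AE form | Smoking | Amount | Next scheduled AE form |
|---|---|---|---|---|
| 1 | step 11a | step 12 | 3 × 2 = 6 puffs | Visit 2, step 6, if the participant returns |
| 2 | step 6 | step 9 | 10 puffs | Visit 3, step 6, if the participant returns |
| 3 | step 6 | step 7 | not fixed; typically 0 to 2 cigarillos | none |

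Two of three sessions have a later scheduled query, for returning participants only.

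**3. Other routes that could reach Visit 3 smoking**

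- Spontaneous report (9.2.1), telling staff of symptoms while smoking (8.1), and the last-visit instruction to report subsequent events believed related (9.1): all are initiated by the participant.
- Follow-up of unresolved events (9.1): applies to events already known.
- Real-time AE monitoring (11.3.1): refers back to the AE section's methods and adds no query.
- Observer and videotape (4.5): the participant is "observed via an observation window by a trained research assistant who will monitor and count the number of cigarillo puffs taken", and "The ad-lib session will be videotaped to independently score the number of puffs taken". The stated purpose of both is puff counting.
- Questionnaires during the session (4.5): participants "periodically complete questionnaires while they wait", but the content is not given.
- SEC Form (9.2.2): named as an AE source document, but neither defined nor scheduled.
- Table 1 (7.3): has no AE row, so it neither adds nor rules out a query.

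**4. How many participants?** Section 7.5 assumes 85% completion and adds 13 recruits to 86; section 5.2 recruits 100 to obtain 86 with complete data.

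- 0.85 × (86 + 13) = 0.85 × 99 = 84.15, about 84
- 0.85 × 100 = 85
- Target: 86

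So about 84 to 86 are expected to complete Visit 3. These are completers. Someone who starts the session and leaves early is exposed but may not be a completer, so the range is not an upper bound on exposure. The only ceiling given is the 100 recruited.

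**5. Is there time for a form?** 90 + 30 = 120 minutes of a visit of about 2.5 hours (150 minutes), which leaves about 150 − 120 = 30 minutes for all other steps.

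**The case against.** The strongest reply is that absence from a visit list proves little here. The Visit 1 list omits the reward ratings taken after each exposure, which are the H1 outcome. The Visit 3 list omits both the periodic questionnaires and the last-visit reporting instruction. Section 8.3.1 delegates procedures to a Manual of Procedures that is not part of the document. A symptom query after smoking may exist. This stands, and it limits the point to what the protocol schedules. A reader might infer that nobody asks about symptoms after the session; the documents do not support so flat a statement.

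A reader might also take Visits 1 and 2 to be fully covered. They are not. A participant who stops after either visit gets no later form, since section 5.7.1 requires no follow-up after withdrawal and section 7.5 assumes that 15% will not complete. For those who return, the form relies on recall within a schedule of two to three weeks. The contrast that remains is that some participants miss the query for Visits 1 and 2, whereas none has one scheduled for Visit 3.

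Finally, the study has no safety objective, the products are commercially available, and participants are in the laboratory throughout the session and the 30 minutes after it, free to speak up and to extinguish the cigarillo. That lowers the importance of the point. It does not supply a query.

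**Conclusion.** The point holds as a minor gap in AE ascertainment. As written, Visit 3 smoking has no scheduled AE query for any participant, about 84 to 86 expected completers and at most the 100 recruited. Capture relies on participant-initiated reports and on general monitoring by the same methods. Mild, brief symptoms may be under-recorded. The documents give no AE rate, so the number missed cannot be estimated and no under-count is shown.

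Three stronger inferences are tempting and unsupported:

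- **That section 7.2.4 contradicts section 9.2.1.** Section 9.2.1 accepts spontaneous reports as a method. The schedule falls short of its aim of capturing all AEs without contradicting it.
- **That Visit 3 is the riskier session.** Its puff number is open, but it may be zero, and nothing in the documents ranks the sessions by risk.
- **That the primary results are affected.** H1 to H3 use ratings, breakpoints and puff counts, none of which depends on the AE form.

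The conclusion assumes that the Visit 3 list runs in time order and that no undescribed instrument already asks about symptoms after smoking.

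**What to change.** In section 7.2.4, add a step after the 30-minute no-smoking period that repeats the existing open-ended AE form, with the window reset to the time since the step 6 form so that events are not recorded twice. If an ad-lib questionnaire or the SEC Form already asks about symptoms after smoking, schedule and define it in section 7.2.4 instead.

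The cost is one short form per participant at Visit 3, about 84 to 86 forms on expected completion, fitted into the roughly 30 minutes of the visit not taken by the session and the no-smoking period. No visit is added. Puff counting has ended by then, so H3 cannot be affected. The change does not make Visit 3 AE counts comparable with those for Visits 1 and 2, which rest on recall at a later visit, and a report by visit should say so.
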